## Study Protocol:

**Project title:** Prognostic Relevance of Fatty Liver Disease for Patients with Chronic Hepatitis B

**Project summary:** Fatty liver disease is increasingly recognized in patients with chronic hepatitis B (CHB). Whether concurrent fatty liver disease affects the long-term outcomes of CHB is unclear. The investigators will perform a longitudinal study to investigate the prognostic relevance of concurrent fatty liver disease for patients with CHB receiving antiviral therapy.

### **Project description:**

**Rationale:** Fatty liver disease has become more prevalent in individuals with CHB, owing to the obesity epidemic. The coexistence of CHB and fatty liver disease, particularly the histologic phenotype of steatohepatitis, can augment liver damage and increase the risk of liver fibrosis. However, there are limited data on the impact of fatty liver disease on clinical outcomes (e.g., cirrhotic complications, hepatocellular carcinoma, need for liver transplantation, and all-cause death) during comprehensive treatment for CHB.

**Objectives:** To determine the long-term effect of concurrent fatty liver disease, particularly a histologic phenotype of steatohepatitis on all-cause mortality and liver-related complications in patients with CHB receiving antiviral therapy at the Faculty of Medicine Siriraj Hospital, Mahidol University, Bangkok, Thailand.

**Methodology:** Retrospective analysis of a prospectively collected database of 408 patients with chronic HBV infection who underwent a liver biopsy for therapeutic decision in initiating antiviral therapy between 2002 and 2008 at Siriraj Hospital, Bangkok, Thailand.

**Data management and analysis:** Prospectively generated liver database that collates clinical, biochemical, and pathological data regarding chronic HBV infection and fatty liver disease. In addition, associated serological results, radiological reports, and patient follow-up/outcomes will

be also reported. Variables will be documented from the date of liver biopsy until either the study outcomes (death, liver transplantation, or liver-related complications), loss of follow-up, or the end of the study period.

Statistical analyses will be done using SPSS version 18.0. Quantitative variables will be compared between groups using standard parametric or non-parametric tests, and qualitative variables will be compared using the Chi-squared test. The cumulative probabilities of mortality or liver transplantation and liver-related complications will be estimated by the Kaplan-Meier method and compared by the log-rank test. Hazard ratios and 95% confidence interval estimates for the outcomes will be calculated by Cox proportional hazard models.

**Ethical considerations:** This study is approved by the Institutional Review Board and is conducted in accordance with the Declaration of Helsinki.

**Gender issues:** None

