COVER PAGE

STATISTICAL ANALYSIS PLAN

**OFFICIAL TITLE: Prognostic Relevance of Fatty Liver Disease for Patients With Chronic
Hepatitis B**

DATE OF DOCUMENT: December 31, 2021

Statistical Analysis Plan

Data will be summarized using descriptive statistics. Quantitative variables will be compared between groups using standard parametric or non-parametric tests, and qualitative variables will be compared using the Chi-squared test. The cumulative probabilities of mortality or liver transplantation and liver-related complications will be estimated by the Kaplan-Meier method and compared by the log-rank test. Hazard ratios (HR) and 95% confidence interval (CI) estimates for the outcomes will be calculated by Cox proportional hazard model. All potential confounders, including age, sex, overweight/obese, diabetes, hypertriglyceridemia, hypertension, and statin use, will be considered for multivariable models to identify independent determinants of the study outcomes. Time at risk will be defined as the date of liver biopsy to the date of outcome or last follow-up. Statistical analyses will be done using SPSS version 18.0.

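### The protocol ends documentation at a liver-related complication, and neither document says that deaths and transplants after one are still counted in the mortality/transplantation analysis

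*Protocol*

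**What the plan says.** The protocol's paragraph on data management and analysis (under Project description) contains the only rule in either document for how long data are captured. Variables are recorded from biopsy "until either the study outcomes (death, liver transplantation, or liver-related complications), loss of follow-up, or the end of the study period". The parenthesis puts a liver-related complication on the same footing as death and transplantation.

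The SAP defines follow-up in one sentence: "Time at risk will be defined as the date of liver biopsy to the date of outcome or last follow-up". It does not say which outcome is meant.

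Both documents treat the two endpoints as distinct. The SAP states: "The cumulative probabilities of mortality or liver transplantation and liver-related complications will be estimated by the Kaplan-Meier method". The log-rank test and Cox models follow for the same outcomes. The protocol's objective is "To determine the long-term effect of concurrent fatty liver disease, particularly a histologic phenotype of steatohepatitis on all-cause mortality and liver-related complications", and its rationale names as clinical outcomes "cirrhotic complications, hepatocellular carcinoma, need for liver transplantation, and all-cause death".

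The data source is described as a "Retrospective analysis of a prospectively collected database of 408 patients with chronic HBV infection".

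**The concern.** An all-cause mortality endpoint needs follow-up that continues through non-fatal events. If documentation stops at the first complication, there are three consequences for the mortality/transplantation analysis.

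- **Lost events.** Deaths and transplants after a complication are not recorded, which costs precision in a cohort of fixed size.
- **A different quantity.** The Cox model estimates the hazard of death or transplantation without a prior complication. Any effect of fatty liver disease on death that runs through complications is cut off, yet the protocol's rationale is that coexisting fatty liver disease worsens liver damage.
- **Informative censoring.** If the hazard of death or transplantation rises after a complication, the patients censored are those at highest risk, and Kaplan-Meier understates the cumulative probability.

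**Working it through.** **Reading the text.** There is no stated event count, event rate or power figure to reproduce. Taken together, the protocol says when recording stops, and the SAP says that time at risk runs to an unspecified outcome. No sentence in either document says that vital or transplant status is recorded after a complication. The word *first* is an inference, but it is the natural reading of a rule that runs until any one of the listed events.

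**Inputs.** From the documents: 408 patients; biopsies 2002 to 2008; SAP dated 31 December 2021. The end of the study period is not dated, so I take t = 2021 − 2008 = 13 years, the shortest follow-up to the SAP date. Everything else is assumed, with constant yearly hazards:

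- a, complication: 0.25% to 2%
- b, death or transplant without complication: 0.5% to 1%
- c, death or transplant after complication: 5% to 20%

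**Formulas (illness-death model).**

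- Event-free probability, full follow-up: S(t) = exp(−(a+b)t) + a[exp(−ct) − exp(−(a+b)t)]/(a+b−c)
- All events: 408 × (1 − S(t))
- Events recorded under the rule: 408 × b/(a+b) × (1 − exp(−(a+b)t))
- Kaplan-Meier risk under the rule: 1 − exp(−bt)

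**Middle case worked through** (a = 0.01, b = 0.01, c = 0.10). exp(−0.26) = 0.7711 and exp(−1.3) = 0.2725, so S = 0.7711 + 0.01 × (0.2725 − 0.7711)/(−0.08) = 0.8334. The true risk is 16.7%, or 68 events. Recorded: 408 × 0.5 × 0.2289 = 47. Kaplan-Meier under the rule: 1 − exp(−0.13) = 12.2%.

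| a, b, c per year | All events | Recorded | Lost | 13-year risk, full | 13-year risk, as written |
|---|---|---|---|---|---|
| 0.25%, 1%, 5% | 52 | 49 | 6% | 12.8% | 12.2% |
| 1%, 1%, 10% | 68 | 47 | 31% | 16.7% | 12.2% |
| 2%, 0.5%, 20% | 83 | 23 | 73% | 20.3% | 6.3% |

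If c = b (no rise in hazard after a complication), Kaplan-Meier is unbiased, although 2% to 12% of events are still lost.

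**Hazard ratios.** These are large-sample Cox solutions with 30% exposed, over 120 combinations of a, b and c spanning the ranges above. The as-written hazard ratio equals the multiplier on b.

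| Exposure effect | Full follow-up | As written |
|---|---|---|
| Doubles complications only | 1.05–1.68 | 1.00 |
| Doubles complications, 1.5-fold on death without complication | 1.51–1.82 | 1.50 |
| Doubles both | 1.85–1.99 | 2.00 |
| Doubles only death without complication | 1.28–1.94 | 2.00 |
| Doubles all three hazards | 2.07–2.63 | 2.00 |
| Doubles only death after complication | 1.04–1.37 | 1.00 |

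At the middle case, doubling complications only gives 1.27 against 1.00; doubling only death without complication gives 1.70 against 2.00. At the low-end case the differences are small (1.05 against 1.00; 1.94 against 2.00).

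Where both hazards are doubled, the 13-year risk difference is 6.4 to 18.0 points with full follow-up and 5.9 to 10.7 as written. The confidence interval for the log hazard ratio is 1.03 to 1.92 times wider (1/√share of events recorded).

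**Sensitivity.** With follow-up uniform over 13 to 20 years, the loss is 8% to 75% and the ends of the hazard ratio ranges move by about 0.02 at most. With 5 years of follow-up, the three cases in the first table lose 3%, 18% and 60%. With 5% yearly dropout over 13 years, the middle case falls from 68 to 49 events and the share lost is 29%.

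**The case against.** The strongest reply is that the protocol sentence governs data capture and is not a censoring rule. Time at risk is defined only in the SAP, with outcome in the singular. With two endpoints analysed separately, that most naturally means the outcome under analysis, and the protocol's parenthesis merely lists the study outcomes. That reading is possible. It does not settle the matter, because it needs deaths and transplants after a complication, which the protocol says are no longer documented.

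Second, this is an existing database, and a sentence in a plan cannot remove what is already held. The protocol also says that "associated serological results, radiological reports, and patient follow-up/outcomes will" be reported. This stands as a limit: actual data loss is not shown. Equally, neither document says that the later data are held.

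Third, every rate is assumed, and the results run from trivial to large with no fixed direction of bias. That is correct. The figures show a mechanism and a plausible range, not an estimate for this cohort. The event counts also ignore loss to follow-up, so they are near an upper bound for 13 years; dropout changes the share lost much less.

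Fourth, it can be doubted that exposure acts on death without a liver complication. The SAP's candidate confounders, "including age, sex, overweight/obese, diabetes, hypertriglyceridemia, hypertension, and statin use", are largely cardiometabolic, but a list of adjustment variables does not establish such an effect. It means only that bias away from 1 cannot be excluded when the outcome is death from any cause.

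**Conclusion.** The concern holds in its conditional form. The only data-capture rule ends at a liver-related complication, mortality or transplantation is a separate endpoint, and nothing in either document reconciles the two.

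If the rule is applied, the mortality/transplantation analysis answers a different question with fewer events: 6% to 73% fewer under the assumed rates at 13 years. Understatement of the Kaplan-Meier risk depends on the hazard rising after a complication. The hazard ratio is biased towards 1 if exposure acts mainly through complications or on mortality after them. It is little changed if exposure acts equally on complications and on death without complication, and biased away from 1 if it acts mainly on the latter.

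If the investigators read the SAP per endpoint and the database holds the later events, the defect is one of wording only. Confidence is medium for that reason. It should be fixed in either case, because the reader cannot tell which situation applies.

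**What to change.** Define follow-up and time at risk separately for each endpoint, in the same words in the protocol and the SAP:

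- **Mortality or transplantation:** from biopsy to death, transplantation, the date last known alive, or a stated data cut-off, regardless of any earlier liver-related complication.
- **Liver-related complications:** from biopsy to first complication, death, transplantation, last follow-up, or the cut-off.

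Report how vital and transplant status after a complication was ascertained, and for how many patients it is missing.

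The cost is one sentence in each document. If the later data are not already in the database, some record extraction or tracing of vital and transplant status is needed. No new patients or procedures are required.

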COVER PAGE

STATISTICAL ANALYSIS PLAN

**OFFICIAL TITLE: Prognostic Relevance of Fatty Liver Disease for Patients With Chronic
Hepatitis B**

DATE OF DOCUMENT: December 31, 2021

Statistical Analysis Plan

Data will be summarized using descriptive statistics. Quantitative variables will be compared between groups using standard parametric or non-parametric tests, and qualitative variables will be compared using the Chi-squared test. The cumulative probabilities of mortality or liver transplantation and liver-related complications will be estimated by the Kaplan-Meier method and compared by the log-rank test. Hazard ratios (HR) and 95% confidence interval (CI) estimates for the outcomes will be calculated by Cox proportional hazard model. All potential confounders, including age, sex, overweight/obese, diabetes, hypertriglyceridemia, hypertension, and statin use, will be considered for multivariable models to identify independent determinants of the study outcomes. Time at risk will be defined as the date of liver biopsy to the date of outcome or last follow-up. Statistical analyses will be done using SPSS version 18.0.

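### Kaplan-Meier is planned for the cumulative probability of liver-related complications with no competing-event method, so absolute risk may be overstated, possibly only slightly

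*SAP*

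**What the plan says.** The SAP's analysis paragraph reads: "The cumulative probabilities of mortality or liver transplantation and liver-related complications will be estimated by the Kaplan-Meier method and compared by the log-rank test". The protocol (Project description, Data management and analysis) repeats the plan: "liver-related complications will be estimated by the Kaplan-Meier method and compared by the log-rank test". Both add Cox models for hazard ratios. Neither mentions competing risks, cumulative incidence functions or cause-specific hazards.

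On follow-up, the SAP says: "Time at risk will be defined as the date of liver biopsy to the date of outcome or last follow-up". The protocol records variables "until either the study outcomes (death, liver transplantation, or liver-related complications), loss of follow-up, or the end of the study period". Neither document says what happens in the complication analysis to a patient who dies or is transplanted without a prior complication.

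The protocol's Objectives name two outcomes, "all-cause mortality and liver-related complications in patients with CHB receiving antiviral therapy". Its Rationale lists "cirrhotic complications, hepatocellular carcinoma, need for liver transplantation, and all-cause death" as examples of clinical outcomes.

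**The concern.** A patient who has died can no longer have a complication. If that patient is censored, Kaplan-Meier treats the death like loss to follow-up and estimates complication risk as though deaths did not remove people from risk. The plan calls its output a cumulative probability, so readers are likely to take it as the chance that a patient will have a complication. That figure would be too high. If competing rates differ between patients with and without fatty liver disease or steatohepatitis, the between-group difference in absolute risk would be distorted as well. The bias is systematic: more patients would not shrink it, and the confidence interval does not reflect it.

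**Working it through.** **Which reading do the documents support?**

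- The Objectives treat mortality and complications as two outcomes.
- The Rationale lists cirrhotic complications and hepatocellular carcinoma apart from transplantation and death.
- The analysis sentence pairs transplantation with mortality, not with complications. This suggests, without establishing, that transplantation is not a component of complications.
- Under the SAP's time-at-risk rule, a patient who dies without a complication would most naturally be censored at death.

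Together these point to a separate complication curve with prior deaths censored. Against this, the protocol lists death, transplantation and complications together as the events that end documentation, so a composite is not excluded.

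**Inputs.** From the documents: 408 patients, "who underwent a liver biopsy for therapeutic decision in initiating antiviral therapy between 2002 and 2008", and a SAP marked "DATE OF DOCUMENT: December 31, 2021". If data run to that date (an assumption; no study end is given), follow-up could reach about 13 years for a biopsy at the end of 2008 and 20 years for one at the start of 2002. The documents give no complication, death or transplantation rate and no group sizes. All rates below are therefore assumed and held constant, and there is no stated figure to reproduce.

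**Formulas.** Let c be the complication hazard, d the hazard of death or transplantation without a prior complication, and t the time in years.

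- One minus Kaplan-Meier, competing events censored: 1 − exp(−c·t)
- Cumulative incidence: c/(c+d) × [1 − exp(−(c+d)·t)]
- Competing event first: d/(c+d) × [1 − exp(−(c+d)·t)]

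**Example, c = 1.5% per year, t = 15.** Kaplan-Meier: 1 − exp(−0.225) = 20.15%. With d = 0.5% per year, cumulative incidence: 0.75 × [1 − exp(−0.30)] = 19.44%.

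| d per year | Cumulative incidence | Excess of Kaplan-Meier (points) |
|---|---|---|
| 0.1% | 20.00% | 0.1 |
| 0.5% | 19.44% | 0.7 |
| 1% | 18.76% | 1.4 |
| 3% (extreme) | 16.36% | 3.8 |

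**Other horizons, same c.** At 13 years Kaplan-Meier gives 17.72% against 17.17% (d = 0.5%) and 16.65% (d = 1%), an excess of 0.5 and 1.1 points. At 20 years it gives 25.92% against 24.73% and 23.61%, an excess of 1.2 and 2.3 points.

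**Other complication rates, t = 15.** For c from 0.5% to 3% per year, the relative excess is 3.5 to 3.8% at d = 0.5% and 7.1 to 7.6% at d = 1%. It hardly depends on c.

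**Scale.** With all 408 patients followed to 15 years, the standard error of the estimate is √(0.2015 × 0.7985 / 408) = 1.99 points. The excess reaches 1 point at d = 0.712% per year, when about 37 of the 408 have a competing event first. It reaches 2 points at d = 1.476% per year, when about 73 have a competing event first and 74 have a complication.

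**Group contrast, t = 15, complication hazard ratio 1.5 (c = 1.5% vs 2.25% per year).** The Kaplan-Meier difference is 8.50 points.

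| d per year, lower-risk vs higher-risk group | Difference in cumulative incidence (points) |
|---|---|
| 0.5% vs 0.5% | 8.22 |
| 0.5% vs 1% | 7.27 |
| 0.5% vs 1.5% | 6.37 |
| 1% vs 0.5% | 8.89 |

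The error can go either way. With an assumed 204/204 split and risks of 19.44% and 27.66%, the standard error of the difference is 4.18 points.

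**The case against.** The strongest reply is that the bias rests on two facts the documents do not state: that complications are analysed separately, and that patients who die first are censored. If the endpoint is a composite, or if no competing event comes first, there is no bias. The study asks about a group effect and answers it with log-rank tests and Cox models, which remain valid as cause-specific comparisons. No absolute-risk target is set. At competing rates of 1% per year or less, the 15-year excess in the example is below one standard error. That standard error is itself optimistic, since patients biopsied in late 2008 could reach only about 13 years and some will be lost to follow-up. Even the least favourable contrast shown moves by 8.50 − 6.37 = 2.1 points, about half its standard error.

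All of this stands, and it limits how much weight the point carries. It does not remove the point. The plan does commit to reporting a cumulative probability of complications, the natural reading makes Kaplan-Meier the wrong estimator for it, and a better estimator is available from outcomes the plan already records.

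**Conclusion.** The concern holds as a conditional one. Neither document provides a competing-event method. On the most natural reading, the planned complication curve is at or above the true cumulative incidence. The size cannot be fixed from the documents. Under the assumed constant hazards in the 1.5% per year example, it is roughly 0.1 to 1.4 points at 15 years for competing rates up to 1% per year, and more with higher rates or longer follow-up. The absolute difference between groups is materially misstated only if competing rates are appreciable, chiefly if they differ by group; the documents neither show nor exclude this. The main group comparison is not affected. This should be fixed because the remedy is cheap, not because the error is known to be large.

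**What to change.** In the SAP:

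1. State whether complications are analysed separately from death, and whether transplantation is a component of them or a competing event.
2. If separate, estimate complication risk with the Aalen-Johansen cumulative incidence function, treating death (and transplantation, if not a component) as competing.
3. Report, by group, the number of competing events before a first complication. This shows whether the difference from Kaplan-Meier matters.
4. Keep the log-rank test and Cox model for complications, labelled as cause-specific.
5. Keep Kaplan-Meier for death or transplantation, and state that follow-up for these continues after a complication. This is a related but distinct matter: read literally, the protocol's Data management and analysis paragraph stops documentation at the first study outcome, which would censor that curve at a complication.

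The cost is a few sentences and a little extra analysis, possibly in software other than the planned SPSS 18.0. Deaths and transplantations are already named as study outcomes, so the complication curve needs no new data. If the separate reading is the intended one and competing events occur, reported complication risks would be somewhat lower. If a composite is intended, one sentence settles the estimator question.

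### The objective is all-cause mortality, but the only mortality endpoint spelled out is death or liver transplantation, and deaths after an earlier outcome may go unrecorded

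*SAP*

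**What the plan says.** The Objectives paragraph of the Protocol asks for the long-term effect of concurrent fatty liver disease "on all-cause mortality and liver-related complications in patients with CHB receiving antiviral therapy". Transplantation is not part of that objective. The Rationale lists it separately from death among the clinical outcomes of interest: "cirrhotic complications, hepatocellular carcinoma, need for liver transplantation, and all-cause death".

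Under Data management and analysis, the Protocol plans: "The cumulative probabilities of mortality or liver transplantation and liver-related complications will be estimated by the Kaplan-Meier method and compared by the log-rank test". The SAP repeats this: "The cumulative probabilities of mortality or liver transplantation and liver-related complications will be estimated by the Kaplan-Meier method", with the same log-rank comparison.

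For the Cox models the SAP is less specific. Hazard ratio "estimates for the outcomes will be calculated by Cox proportional hazard model", and the listed confounders "will be considered for multivariable models to identify independent determinants of the study outcomes". Neither sentence itemises the outcomes. The one place that does is the Protocol's documentation rule, under which variables are recorded from biopsy "until either the study outcomes (death, liver transplantation, or liver-related complications), loss of follow-up, or the end of the study period". The SAP starts time at risk at biopsy and ends it at the outcome or when follow-up stops. Neither document says what happens to a patient's death time after transplantation or after a complication.

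**The concern.** The question asked and the endpoint spelled out differ. An analysis of death or transplantation describes transplant-free survival. If fatty liver disease relates to transplantation differently from how it relates to death, the combined hazard ratio departs from the mortality hazard ratio, in either direction. Transplantation requires candidacy and access as well as severe disease, so there is no guarantee that the two move together. That is general reasoning, not something the documents state.

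Two further things are at stake. First, this is a retrospective analysis of an existing database. Leaving open whether death is modelled alone, and how transplantation is then handled (censored, treated as a competing event, or followed through), allows the choice to be made after results are seen. Second, if recording stops at the first outcome of any kind, the data may not contain the deaths needed for the stated objective. Patients with a liver-related complication are plausibly at higher risk of death than those without, so such a loss could be informative.

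**Working it through.** The documents give no event counts, hazard ratios, power or significance level, and 408 is the size of the existing database, not a calculated sample size. There is no plan figure to reproduce. The check is a comparison of texts followed by an illustration.

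**Texts side by side**

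| Place | Mortality outcome |
|---|---|
| Protocol, Objectives | All-cause death; no transplantation |
| Protocol, Rationale | Death and transplantation as separate items |
| Protocol, documentation rule | Death, transplantation, complications as separate items; recording ends at any of them |
| Protocol and SAP, Kaplan-Meier and log-rank | Death or transplantation, combined |
| SAP, Cox and multivariable models | Not itemised |

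The Kaplan-Meier sentence most naturally means one combined endpoint plus complications. The Cox sentences have two possible antecedents. If they point back to the Kaplan-Meier sentence just before them, every mortality model is for the composite. If they point to the Protocol's list of study outcomes, death has its own model. The text does not settle which.

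**Documentation rule.** Consider a patient who has a complication and dies later. Read literally, recording ended at the complication, so the death is missing from a death-alone analysis and from the composite as well. For a patient transplanted first who dies later, the composite has its event, but a death-alone analysis misses the death. The number of such patients cannot be derived from the documents.

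**Size of the endpoint difference (assumed inputs).** Let *s* be the share of transplants among first events (death or transplantation) in patients without fatty liver disease. With constant hazards,

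HR(composite) = (1 − s) × HR(death) + s × HR(transplant).

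Take HR(death) = 1.30 and HR(transplant) from 0.5 to 3.0.

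- s = 5%: 0.95 × 1.30 = 1.235. Lower end 1.235 + 0.05 × 0.5 = 1.26; upper end 1.235 + 0.05 × 3.0 = 1.385.
- s = 20%: 0.80 × 1.30 = 1.04. Lower end 1.04 + 0.20 × 0.5 = 1.14; upper end 1.04 + 0.20 × 3.0 = 1.64.

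HR(death) in this formula is for death before transplantation. The illustration does not cover deaths lost after a complication.

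**The case against.** The strongest reply is that the composite is legitimate and grounded in the Protocol, which names transplantation as an outcome of interest in both the Rationale and the list of study outcomes. All-cause death is a component of it, so mortality is not absent from the plan. If transplants are few, the composite is nearly a mortality analysis: at a 5% share the illustrated ratio stays between 1.26 and 1.385 around 1.30. Age, overweight or obesity, diabetes, hypertriglyceridemia and hypertension, through which access to transplantation might differ between groups, are on the SAP's list of candidate confounders.

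Much of this stands. It limits the likely size of the problem and makes rewording the objective to match the composite a valid alternative to a new analysis. It does not remove the mismatch. Adjustment can reduce differences arising through the listed covariates, but it leaves the endpoint unchanged and does not reach the Kaplan-Meier curves or the log-rank test. The documents also do not say that transplants are rare.

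A reader might infer that the plan never estimates all-cause mortality. The documents do not support that: the Cox sentences are open, and the Protocol lists death as its own study outcome. Nor do they support a claim that the composite will seriously misstate the mortality effect, since the wide range needs a 20% transplant share together with an extreme transplant hazard ratio, both assumed. The literal reading of the documentation rule is also not certain to match practice; the database may hold later deaths.

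**Conclusion.** The point holds as a gap in specification. The objective names all-cause mortality; the only mortality endpoint explicitly specified is death or liver transplantation; and whether death alone is modelled, and how transplantation is then handled, is not stated. Read literally, the documentation rule adds a data problem, because deaths after a transplant or a complication would not be captured.

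A composite hazard ratio does not by itself establish an effect on all-cause mortality. How close it comes depends on the unknown transplant share and on the transplant hazard ratio. Under the constant-hazards assumption and the illustrative inputs, the departure from 1.30 is at most 0.085 at a 5% share (1.385 − 1.30) and at most 0.34 at 20% (1.64 − 1.30). The loss of later deaths cannot be sized from the documents. This should be corrected, but it does not invalidate the design.

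**What to change.** - Name all-cause death from biopsy as an explicit Kaplan-Meier and Cox endpoint, counting deaths after transplantation and after liver-related complications.
- Amend the Protocol's documentation rule so that vital status is taken to last follow-up regardless of earlier outcomes.
- Keep death or transplantation as a labelled second endpoint, list the endpoint of every Cox model, and report the number of deaths and transplants by exposure group.
- Base any conclusion about mortality on the death-alone model. If later deaths cannot be retrieved, restate the objective and the conclusion as death or transplantation.

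The analysis cost is one more curve and one more Cox model. Death alone will have somewhat fewer events than the composite, hence a wider interval. If recording did stop at the first outcome, vital status will also have to be retrieved from existing records for the patients affected.

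### Does recording covariates up to the outcome bring immortal time into the Cox model and bias the fatty-liver hazard ratio?

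*SAP*

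**What the plan says.** The SAP, a single paragraph, sets the clock: "Time at risk will be defined as the date of liver biopsy to the date of outcome or last follow-up". Hazard ratios "will be calculated by Cox proportional hazard model", and the candidate covariates follow, introduced as potential confounders: age, sex, overweight or obesity, diabetes, and then "hypertriglyceridemia, hypertension, and statin use, will be considered for multivariable models to identify independent determinants of the study outcomes". It gives no measurement date for them, no distinction between use at biopsy and use at any time, and no time-dependent term.

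The protocol's Data management and analysis paragraph has the only statement on when data are captured: "Variables will be documented from the date of liver biopsy until either the study outcomes", loss to follow-up or the end of the study. The exposure, in the Objectives, is "concurrent fatty liver disease, particularly a histologic phenotype of steatohepatitis on all-cause mortality and liver-related complications". The Methodology paragraph describes a "Retrospective analysis of a prospectively collected database of 408 patients with chronic HBV infection", each of whom had a "liver biopsy for therapeutic decision in initiating antiviral therapy between 2002 and 2008".

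**The concern.** Statins, diabetes, hypertension and hypertriglyceridemia can all begin years after biopsy, and follow-up is long. Someone who starts a statin in year eight must have been event-free for eight years. If that person is a user from day zero in the model, those eight years count as exposed time in which no event could have occurred. This is immortal time, and it makes the statin look protective whatever its real effect.

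The error can pass to the main comparison. If fatty-liver patients start statins more often, the model credits them with a benefit that does not exist, and the adjusted fatty-liver HR rises to compensate. At stake would be a spurious harmful effect of fatty liver and a false report of statins as an independent determinant of outcome, which is a kind of result the SAP sets out to produce.

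**Working it through.** Neither document has a sample size, power or event calculation, so there is no figure of the plan to reproduce. The check has three parts: what the text prescribes, what the harmful coding would do, and how that compares with the study's precision.

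**1. Reading the text.** Bias in the fatty-liver HR needs three conditions together.

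| Condition | What the documents say |
|---|---|
| Starts after biopsy are coded as fixed from time zero | Not stated; the protocol sentence describes the collection window of the database, which includes the biopsy date and must run to the outcome because outcomes are collected too |
| The variable stays in the final model | Not stated; covariates are only to be considered |
| Uptake differs by fatty-liver status | Plausible, but no figures given |

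The SAP calls the variables potential confounders. The exposure is histology at biopsy, so a confounder must already be present by then. A statin begun later cannot confound a biopsy finding.

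**2. Simulation of the harmful coding.**

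*Inputs from the documents:* 408 patients; biopsies 2002 to 2008; time zero at biopsy; ordinary Cox model.

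*Assumptions:* the end of study is undated, so the SAP date (end of 2021) stands in, giving 2021 − 2008 = 13 to 2021 − 2002 = 19 years. Outcome rate 0.7 to 1.5 per 100 person-years; fatty liver in 30% to 50%; statin starts 2 per 100 person-years without fatty liver and 2, 4, 6 or 8 with it; true statin HR 1; true fatty-liver HR 1.0, 1.5 or 2.0.

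*Models,* with F for fatty liver:
- (a) log hazard = baseline + βF
- (b) as (a), plus γ × (any statin use in follow-up), entered as fixed
- (c) as (a), plus γ × (statin already started by time t)
- (d) as (a), plus γ × (statin use at biopsy)

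Results with 200,000 patients per scenario:

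| Uptake ratio, fatty liver vs none | Fatty-liver HR in (b) ÷ HR in (a) |
|---|---|
| 1 | 0.99–1.00 |
| 2 | 1.14–1.16 |
| 3 | 1.29–1.35 |
| 4 | 1.47–1.56 |

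Across these scenarios the statin HR in (b) is 0.33 to 0.46, against a truth of 1. Model (c) returns a fatty-liver HR of 0.98 to 1.03 when the truth is 1.0. Model (d), run with two levels of use at biopsy (5% vs 15% and 10% vs 30%) and no later starts, gives fatty-liver HRs of 1.000 and 0.994 and statin HRs of 1.016 and 1.005.

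A separate simulation used other assumed rates: 40% exposed, 9 to 17 years of follow-up and 1% to 2% events per year. It gave fatty-liver HRs of 1.13 to 1.14 for starts of 1% vs 3% per year, and 1.31 to 1.32 for 1.5% vs 6%. Without the statin term the HR was 1.00 to 1.01.

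**3. Size against precision.** In 1,000 data sets of 408 patients (40% exposed, 1 outcome per 100 person-years, true HR 1.0, about 60 events), the geometric mean fatty-liver HR under (b) was 0.99, 1.16 and 1.31 for uptake ratios 1, 2 and 3. With d events and exposed share p, SE(log HR) ≈ 1/√[d·p·(1 − p)].

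- d = 60, p = 0.4: 1/√14.4 = 0.26. The shifts are ln 1.16 / 0.26 = 0.148/0.26 ≈ 0.6 SE and ln 1.31 / 0.26 = 0.270/0.26 ≈ 1.0 SE.
- At the lower outcome rate, 408 × 0.106 ≈ 43 events: SE 0.31, shifts about 0.5 and 0.9 SE.
- At the higher rate, 408 × 0.213 ≈ 87 events: SE 0.22, shifts about 0.7 and 1.2 SE.

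**The case for a change.** The strongest reply is that a plan open to both a sound coding and a biased one should choose between them. The only timing statement in either document covers the follow-up period. The analysis is retrospective, so the coding may be chosen with outcomes already on record. Follow-up could approach two decades. The false statin effect does not even need differential uptake: at equal start rates the statin HR is still about 0.45.

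Much of this stands. The measurement date is missing, the mechanism is real, and a bias of up to about one standard error or more would not be negligible if it arose. What does not stand is the step from a silent plan to a biased one. The word ever appears nowhere, and the collection-window sentence does not say which value enters the model. Taking confounders at time zero is routine in a Cox model that starts at biopsy.

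A related argument is that leaving out later statin use has a cost of its own. In one scenario with a protective statin (HR 0.7) and threefold uptake, the model without it gives a fatty-liver HR of 0.92. But that is the total effect of fatty liver, including the treatment it leads to, and it is a legitimate answer to a prognostic question. Time-dependent modelling answers a different question and needs start dates that neither document says are recorded.

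**Conclusion.** The concern does not call for a change. The documents leave the covariate measurement date unstated; they do not prescribe coding from follow-up. Under the ordinary reading, status at biopsy, there is no immortal time and the fatty-liver HR is unaffected (0.99 to 1.00 in simulation, truth 1.0). The Kaplan-Meier and log-rank comparisons do not use these covariates, and age and sex are not open to the problem.

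Only if all three conditions held would the fatty-liver HR be inflated, by a factor of about 1.15 at twofold and 1.3 at threefold uptake, or roughly 0.5 to 1.2 standard errors at 43 to 87 events. With equal uptake the factor is about 1.0. Every rate behind these figures is assumed, and only statins were simulated, so the sizes are illustrative and were not computed for diabetes, hypertension or hypertriglyceridemia. What remains is a gap in wording that a competent analyst fills correctly by default.
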